2.3 Study Subjects

Demographic endpoints and subject characteristics will be summarized using descriptive statistics using the Observed Cases (OC). There are no planned inferential statistical analyses of demographic endpoints or subject characteristics.

2.3.1 Subject Disposition

The number of subjects who are eligible to enter the extension study will be reported in total and by study center.

The number of subjects who enter the extension study, complete the study, and withdraw will also be summarized in total and by study center. The primary reasons for not participating in the study or completing the study will be summarized by reason.

The number of subjects expected, completed, missed, and withdrawn will be summarized by scheduled visit.

- Expected = all subjects minus withdrawn subjects.
- Completed = subjects that showed up at that visit.
- Missed = expected subjects minus completed subjects.
- Withdrawn = all subjects who have withdrawn up to that visit.

All withdrawn subjects will be listed individually, by subject number, date and reason for withdrawal, and last visit performed.

2.3.2 Protocol Deviations

Subjects with any protocol deviations occurring during the extension study, as well as type of deviation, will be summarized by treatment group (Group A or Group B), overall and by site. Separate summaries will be provided for COVID-19 related protocol deviations.

2.3.3 Demographic and Pre-treatment Characteristics

[figure not shown]
Pre-treatment age, weight, and body mass index (BMI) will be summarized as continuous variables.

Gender, age category (≥ 55 vs < 55), race, ethnicity, Fitzpatrick skin type, pre-treatment GCWS [REDACTED] [REDACTED] for both Blinded Evaluator and Treating Investigators, reporting for each side of the face) will be summarized as categorical variables.

Demographics will be summarized for each treatment group.

2.3.4 Medical History, Medications, and Procedures

Prior and concomitant medications will be coded using the World Health Organization Drug Dictionary (WHODD). Medical history, and prior and concomitant procedures/non-pharmacological treatments will be coded according to MedDRA.

Effective date: 2022-03-08 18:10

Version: 2.0

Effective

Prior medications/procedures are the medications/procedures with stop dates prior to the Month 12 visit. Medications/procedures will be considered concomitant as follows:

- Any therapy ongoing at the time the subject exited study 43USSA1812, Month 12.
- Any changes to existing therapies (such as changes in dose or formulation) during the course of the study
- Any new therapies started after exiting study 43USSA1812 Month 12.

Subjects reporting medical history, cosmetic treatments/procedures, and prior and concomitant procedures/non-pharmacological treatments will be summarized by system organ class (SOC) and Preferred Term (PT). A separate summary of medical history occurring in at least 5% of subjects will be provided.

Subjects reporting prior and concomitant medications will be summarized separately, by WHODD Anatomical Therapeutic Chemical (ATC) Class Level 3 (if Level 3 is not available, the highest class available will be used) and WHODD generic name.

2.4 Effectiveness Analysis

2.4.1 Datasets Analyzed

All analyses will be performed on the extension population.

2.4.2 Efficacy Analyses

Pre-treatment refers to the Month 12 (pre-treatment) visit for Group A subjects (originally randomized to control group in pivotal study 43USSA1812). For Group B, pre-treatment refers to Day 1 which occurred during the 43USSA1812.

Effectiveness endpoints will be analyzed by treatment group as follows:

- The following proportions will be summarized and report exact 2-sided 95% confidence intervals (Clopper-Pearson method):
 - GCWS [REDACTED] responder rate, as assessed live by the Blinded Evaluator at Months 19, 21 and 24. A responder is defined as a subject with at least 1 grade improvement from pre-treatment on both cheeks concurrently. Summaries will be provided overall, by age group (<55 vs. \geq 55), and Fitzpatrick skin type (FST) group (I-III vs. IV-VI).
 - Percentage of subjects having at least “Improved” according to the GAIS on both sides of the face combined, as assessed live by the subject and the Treating Investigator separately, at all visits following Month 12 in the pivotal study 43USSA1812.
- Percentage of subjects responding in each response category for each question in the subject satisfaction questionnaire at all visits following Month 12 in the pivotal study 43USSA1812

(no confidence intervals will be provided).

- Change from pre-treatment in subject satisfaction using the Satisfaction with Cheeks FACE-Q questionnaire with Outcome Rasch transformed will be summarized with descriptive statistics and 2-sided exact 95% confidence intervals (via t-distribution). Total Rasch transformed scores as well as proportion of subjects in each response category for each of the individual questions at all visits following Month 12 in pivotal study 43USSA1812.
- Time to return to social engagement after treatment (based on subject diaries, Group A only) will be analyzed using Kaplan-Meier methods. The median time to return to social engagement will be estimated and Kaplan-Meier plots will be created.

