4.1 General outline

This is a 12-month extension of the prospective, randomized, evaluator- blinded, no-treatment controlled study 43USSA1812.

[figure not shown]
Subjects originally randomized to Control Group (approximately 50 subjects) in the pivotal study will be offered treatment with *Sculptra Aesthetic* in the extension study. This group of subjects is designated as **Group A** within this protocol.

Subjects originally randomized to Treatment Group (approximately 100 subjects) in the pivotal study will be continued to be followed up during the extension study without further treatment. This group of subjects is designated as **Group B** within this protocol.

Safety and effectiveness data will be collected for up to 24 months in subjects randomized to the Treatment Group (who are not treated in the extension study) and for up to 12 months in subjects randomized to the Control Group (who are treated in the extension study). In all, subjects will be followed for 24 months after the baseline visit in the pivotal study.

Note: One month is defined as 4 weeks in the study.

Effective date: 2020-07-29 18:26

Figure 1. Study Flow Chart

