4.7 Visits

Table 1. Schedule of events, Group A (subjects receiving Treatment in 43USSA1812ext)

	Visit 5 ¹ Final Study Visit 43USSA1812	Visit 1 ² Extension Study Entry Treatment 1	Visit 1a: Telephone Contact	Visit 2: Month 13 Treatment 2 ⁶ (Optional)	Visit 2a: Telephone Contact ⁷	Visit 3: Month 14 Treatment 3 ⁶ (Optional)	Visit 3a: Telephone Contact ⁷	Visit 4: Month 15 Treatment 4 ⁶ (Optional)	Visit 4a: Telephone Contact ⁷	Visit 5: Month 19 Follow-up	Visit 6: Month 21 Follow-up	Visit 7: Month 24 Final visit/ Early termination
	Month 12 (±2 weeks) after Baseline (+2 weeks) after Visit 5		72 hours (±24 hrs) after Treatment 1	1 month (±2 weeks) after Treatment 1	72 hours (±24 hrs) after Treatment 2	1 month (±2 weeks) after Treatment 2	72 hours (±24 hrs) after Treatment 3	1 month (±2 weeks) after Treatment 3	72 hours (±24 hrs) after Treatment 4	7 months (±2 weeks) after ext. Visit 1	9 months (±2 weeks) after ext. Visit 1	12 months (±2 weeks) after ext. Visit 1
Informed consent		X										
Inclusion/Exclusion criteria		X ⁴		X ⁴		X ⁴		X ⁴				
Demographics incl. weight	X	X ³								X ³	X ³	X ³
Concomitant therapies	X	X	X	X	X	X	X	X	X	X	X	X
Urine pregnancy test ^{4,5}		X		X		X		X				
Photography (2D and 3D)	X	X ⁴		X ⁴		X ⁴		X ⁴		X	X	X
Sculptra Aesthetic administration		X		X ⁶		X ⁶		X ⁶				
Adverse event assessment	X	X	X	X	X	X	X	X	X	X	X	X
Safety Assessments ¹¹	X	X		X		X		X		X	X	X
Visual function assessments ⁹	X	X ^{4,10}		X ^{4,10}		X ^{4,10}		X ^{4,10}		X	X	X
Device deficiencies		X		X ⁸		X ⁸		X ⁸				
Dispense subject diary		X		X ⁸		X ⁸		X ⁸				
Collect subject diary				X ⁴		X ^{4,7}		X ^{4,7}		X ⁷		
Treating Investigator Assessments												
GAIS	X	X ⁴		X ⁴		X ⁴		X ⁴		X	X	X
CCI		X ⁴		X ⁴		X ⁴		X ⁴				
	X	X ⁴								X	X	X
Blinded Evaluator Assessments												
CCI	X	X ⁴								X	X	X
Subject Assessments												
GAIS	X	X ⁴		X ⁴		X ⁴		X ⁴		X	X	X
Subject satisfaction questionnaire				X ⁴		X ⁴		X ⁴		X	X	X
FACE-Q	X	X ⁴		X ⁴		X ⁴		X ⁴		X	X	X

1. Visit 5 is identical to Visit 5 outlined and performed in the pivotal study 43USSA1812.
2. 43USSA1812ext Visit 1 can be performed at Visit 5 (Month 12, pivotal study) or as a separate visit within 2 weeks of Visit 5 (Month 12, pivotal study). When Visit 1 extension occurs on the same day as Visit 5 pivotal (Month 12 in 43USSA1812), assessments already outlined in Visit 5 study protocol 43USSA1812 only need to be performed once.

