3. Weight only
4. Pre-treatment
5. Females of childbearing potential

6. If treatment is not performed this is a follow up visit
7. If applicable (i.e. if treatment was performed at the previous visit)
8. If applicable (i.e. if treatment is performed at this visit)
9. Visual Function assessments include: Snellen visual acuity test, Extraocular muscle function test, Confrontation visual field
10. 30 minutes post treatment
11. Safety assessments include: Cheek firmness, symmetry and function, Device palpability (pre-treatment assessment excluded), Mass formation, Cheek sensation

Abbreviations: GAIS (Global Aesthetic Improvement Scale), CCI [REDACTED] ET (Early Termination)

Table 2. Schedule of events, Group B (subjects originally randomized to Treatment Group in 43USSA1812)

	Visit 8 ¹ Final Study Visit 43USSA1812	Visit 1: Extension Study Entry ² Visit	Visit 2: Month 19 Follow up Visit	Visit 3: Month 21 Follow up Visit	Visit 4: Month 24 Final visit/Early termination Visit
	Month 12 (±2 weeks) after Baseline	Month 12 (+2 weeks) after Visit 8	7 months (+2 weeks) after ext. study Visit 1	9 months (±2 weeks) after ext. study Visit 1	12 months (±2 weeks) after ext. study Visit 1
Informed consent	X	X			
Inclusion/Exclusion criteria	X	X			
Concomitant therapies	X	X	X	X	X
Demographics incl. weight	X	X ⁴	X ⁴	X ⁴	X ⁴
Photography (2D and 3D)	X	X	X	X	X
Adverse event assessments	X	X	X	X	X
Safety assessments ³	X	X	X	X	X
Treating Investigator Assessments					
GAIS	X	X	X	X	X
	X	X	X	X	X
Blinded Evaluator Assessments					
CCI	X	X	X	X	X
Subject Assessments					
GAIS	X	X	X	X	X
Subject Satisfaction questionnaire	X	X	X	X	X
FACE-Q	X	X	X	X	X

1. Visit 8 is identical to Visit 8 outlined and performed in the pivotal study 43USSA1812.

2. 43USSA1812 ext Visit 1 can be performed at Visit 8 (Month 12, pivotal study) or as a separate visit within 2 weeks of Visit 8 (Month 12, pivotal study).

When Visit 1 extension occurs on the same day as Visit 8 pivotal (Month 12 in 43USSA1812), assessments already outlined in Visit 8 study protocol 43USSA1812 only need to be performed once.

3. Extension study Safety assessments include: Cheek firmness, symmetry and function, Device palpability, Mass formation, Cheek sensation (Visual Function assessment for pivotal study final study visit [Visit 8] only).

4. Weight only

Abbreviations: GAIS (Global Aesthetic Improvement Scale), CCI [REDACTED] ET (Early Termination)

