10.4 Effectiveness analysis

Pre-treatment is defined as Month 12 (pre-treatment) for Group A subjects and Day 1 in pivotal study 43USSA1812 for Group B subjects.

Change from pre-treatment is calculated as the value *minus* the pre-treatment value.

Exact confidence intervals will be used for the proportions, i.e. they will be based on the binomial distribution. For the presentation of effectiveness data, all time points from pre-treatment through the end of the extension study will be presented for the extension population. Group A data may be compared to Group B data descriptively.

CCI

Responder rate based on the CCI [REDACTED], as assessed live by the Blinded Evaluator at Months 19, 21 and 24 will be analyzed as effectiveness endpoints.

A responder is defined as a subject with at least 1 grade improvement from pre-treatment on both cheek concurrently.

GAIS

Responder rate based on the GAIS, as assessed live by the subject and Treating Investigator separately at Month 19, 21 and 24 will be analyzed as effectiveness endpoints.

A responder is defined as a subject having at least "Improved" according to the GAIS on both sides of the face combined.

Time to return to social engagement after treatment based on subject diaries

Return to social engagement will be analyzed using Kaplan-Meier methods. The median time to return to social engagement will be estimated and Kaplan-Meier plots will be created.

Other effectiveness endpoints

All other effectiveness endpoints will be analyzed by the means of standard descriptive statistics, including 95% confidence intervals.

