1.1.1 Study Design

This is a 12-month extension of the prospective, randomized, evaluator-blinded, no-treatment controlled study 43USSA1812.

Subjects originally randomized to Control Group (approximately 50 subjects) in the pivotal study will be offered treatment with *Sculptra Aesthetic* in the extension study. This group of subjects is designated as **Group A** within this protocol and this statistical analysis plan.

Subjects originally randomized to Treatment Group (approximately 100 subjects) in the pivotal study will be continued to be followed up during the extension study without further treatment. This group of subjects is designated as **Group B**.

A summary or comparison by treatment group means by Group A vs. Group B status.

Safety and effectiveness data will be collected for up to 24 months in subjects randomized to the Treatment Group (Group B) (who are not treated in the extension study) and for up to 12 months in subjects randomized to the Control Group (Group A) (who are treated in the extension study). In all, subjects will be followed for 24 months after the baseline visit in the pivotal study, with post-treatment safety and effectiveness data collected for up to 12 months in both Group A and B.

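### Does the SAP need a table aligned on time since first injection, given that Groups A and B are 48 weeks apart at Months 19, 21 and 24?

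*SAP*

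**What the plan says.** SAP 2.4.2 opens with "Effectiveness endpoints will be analyzed by treatment group as follows", and SAP 1.1.1 explains that "A summary or comparison by treatment group means by Group A vs. Group B status". For the wrinkle scale, SAP 2.4.2 lists the Blinded Evaluator's "responder rate, as assessed live by the Blinded Evaluator at Months 19, 21 and 24", with Clopper-Pearson intervals. Each group has its own reference visit: Month 12 before treatment for Group A, Day 1 of the pivotal study for Group B.

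Protocol 10.4 names the same three months for this endpoint. It adds that "all time points from pre-treatment through the end of the extension study will be presented for the extension population" and that "Group A data may be compared to Group B data descriptively". The SAP does not repeat the sentence on all time points. SAP 2.1 gives the SAP precedence over the protocol's statistical sections only where the two differ.

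On timing, Protocol 4.1 notes: "One month is defined as 4 weeks in the study". Table 1 in Protocol 4.7 places Group A's last visit at "12 months (±2 weeks) after ext. Visit 1". Table 2 places Group B's final pivotal visit at "Month 12 (±2 weeks) after Baseline" and marks a Blinded Evaluator assessment both there and at extension entry.

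**The concern.** The groups share month labels but not treatment clocks. Group A starts its injections at extension Visit 1 (Protocol 6.5.2). Group B is not treated again. Adjacent Month 24 columns therefore show Group A about a year after starting treatment and Group B about two study years after.

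Duration of effect is what the extension sets out to describe (Protocol 2.3), and Protocol 6.5.4 expects the implant to degrade. If a reader took the columns as like for like, a lower rate in Group B could be put down to the group when it reflects elapsed time, or a real group difference could be hidden. The visit that would separate these, Group B at Month 12, is scheduled and rated but is not among the GCWS months in SAP 2.4.2. The SAP also names no display by time since first injection.

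**Working it through.** **Inputs.** One month is 4 weeks (Protocol 4.1). Group A's first injection is at extension Visit 1 (Protocol 6.5.2). Group B's first injection is taken as Day 1, because SAP 1.3 sets its pre-treatment visit there; the pivotal protocol is not among the documents, so this is an assumption. Visit windows come from Protocol 4.7 and the SAP's schedule of events.

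**Reproducing the plan's own figures.** Month 12 to Month 24 is (24 − 12) × 4 = 48 weeks, as in the Protocol synopsis. Adding 2 weeks for entry and 2 for the last visit gives 52, as in Protocol 4.3.

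**Nominal weeks since first injection.** Group A = (month − 12) × 4; Group B = month × 4.

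| Visit | Group A | Group B | Gap |
|---|---|---|---|
| Month 19 | 28 | 76 | 48 |
| Month 21 | 36 | 84 | 48 |
| Month 24 | 48 | 96 | 48 |

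**With windows.** Group B enters the extension at 48 ± 2 weeks plus 0 to 2, that is 46 to 52 weeks after Day 1.

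- Month 24: Group A 46 to 50; Group B 46 + 46 = 92 to 52 + 50 = 102. Gap 92 − 50 = 42 to 102 − 46 = 56.
- Month 21: Group A 34 to 38; Group B 80 to 90. Gap 42 to 56.
- Month 19 with the +2-week window of Protocol 4.7.9 and 4.7.10: Group A 28 to 30; Group B 74 to 82. Gap 44 to 54. The SAP's schedule prints ±2 weeks for both groups, which gives Group A 26 to 30, Group B 72 to 82, and a gap of 42 to 56.

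**Aligned pair.** Group A at Month 24 is 46 to 50 weeks. Group B is 46 to 50 at the pivotal Month 12 visit, or 46 to 52 at extension entry. The nominal gap is 0, with a range of −4 to +4 weeks, or −4 to +6 using entry.

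**What the aligned pair could show.** With 50 and 100 subjects, no dropout and a common assumed rate p, the half-width of the 95% interval for the difference is 1.96 × √[p(1 − p)(1/50 + 1/100)]:

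- p = 0.6: 1.96 × √0.0072 = 16.6 points
- p = 0.8: 1.96 × √0.0048 = 13.6 points
- p = 0.9: 1.96 × √0.0027 = 10.2 points

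**Separating group from time.** For the reported rates, A(M24) − B(M24) = [A(M24) − B(M12)] + [B(M12) − B(M24)]. The algebra is exact. The second bracket is Group B's change over time only if the same subjects are seen at both visits. SAP 2.1.4 uses observed cases, so denominators can differ and that bracket can mix change with dropout.

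**Is Month 12 for Group B omitted?** Protocol 10.4 contains both the three-month endpoint list and the commitment to show all time points, so in the protocol the list does not exclude other visits. The SAP repeats the list and is silent on the commitment. Silence is not clearly a difference that would trigger the SAP's precedence rule. Group B's range starts at Day 1, so Month 12 lies within it.

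**The case for a change.** The best case for acting is that the SAP governs the analysis, lists three GCWS months, and omits the protocol's wider commitment. A programmer working from the SAP alone might produce only those three. Even with every time point shown, nothing tells the reader to line the groups up by time since injection. SAP 1.1.1 adds to the risk: after giving 24 months of data for Group B and 12 for Group A, it closes by describing post-treatment data of up to 12 months in both groups. One extra table and a column label, from visits already scheduled, would cost little.

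The 48-week offset stands, and so does the absence of Group B's Month 12 rate from the visible list. The step to a needed change does not. The protocol only permits a descriptive comparison and names no month for it. The differing reference visits are stated several times in both documents. SAP 2.1.2 leaves table formats to a companion document and lets supportive analyses be added and described in the study report without an amendment, so a useful side-by-side display needs no new plan text. Absence also cannot be fully established: the exploratory sections (SAP 1.4.1 and 2.4.3) are not visible and the table formats were not available.

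The proposed substitute has faults of its own. Group A had an untreated year and had the exclusion criteria applied again. Group B's Month 12 was rated while Group A was still untreated. Group A may have one to four sessions, so alignment on first injection does not align time since the last one. Directing every comparison to that pair would exchange one confounded reading for another.

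**Conclusion.** No change is called for. The groups are a nominal 48 weeks apart at every listed GCWS visit (about 42 to 56 weeks with the SAP's printed windows), so month-matched columns should not be read as a treatment comparison. The plan does not make that comparison: it contains no between-group test or contrast. Each group's responder rate against its own pre-treatment visit, with its exact interval, answers the long-term effectiveness objective and would be the same with or without an aligned table. Group B's Month 12 value is collected and falls under the protocol's commitment to show all time points. Printing weeks since first injection beside the month labels is ordinary care in reporting that analysts can take without new plan text.

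This rests on Day 1 being Group B's first injection, on the SAP's silence not overriding Protocol 10.4, and on the visible text only. The documents give no response rates, so the size of any apparent difference between the groups at a shared month is unknown. The conclusion would change if the report were to draw a claim from the difference between the groups at the same month label.

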2.3 Study rationale and justification for design

This study is an extension of study 43USSA1812, which evaluated the effectiveness and safety of *Sculptra Aesthetic* for treatment of cheek wrinkles, with the objective of an expanded label indication. The purpose of this extension of the study is to evaluate long-term safety and effectiveness data of *Sculptra Aesthetic* beyond the Month 12 duration of the pivotal study 43USSA1812, to help characterize the long-term safety and effectiveness profile of the more dilute suspension.

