2.1 General Methods

Any change made to the finalized SAP before database lock will result in a SAP amendment. Otherwise, the change will be documented in the Clinical Study Report (CSR).

Some of the analyses detailed here may be more explicit or in some aspects different from those stated in the protocol. In case of differences, this SAP supersedes the statistical sections in the protocol.

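### Does the SAP leave Group B's Month 12 result out of the extension analysis, so that durability after Month 12 cannot be read?

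*SAP*

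**What the plan says.** SAP section 2.4.2 reports, by group, the GCWS "responder rate, as assessed live by the Blinded Evaluator at Months 19, 21 and 24", with exact 95% intervals. GAIS, the satisfaction questionnaire and FACE-Q are reported "at all visits following Month 12 in the pivotal study 43USSA1812". Pre-treatment is Day 1 of the pivotal study for Group B and Month 12 for Group A. SAP section 1.3 adds that the extension entry visit is the pre-treatment visit for Group A but not for Group B.

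Protocol section 10.4 gives the same GCWS months. It also has a general presentation rule for effectiveness data: "all time points from pre-treatment through the end of the extension study will be presented for the extension population". The SAP does not repeat that sentence. On precedence, SAP section 2.1 says: "In case of differences, this SAP supersedes the statistical sections in the protocol".

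In the Group B schedule (protocol section 4.7, Table 2), the last pivotal visit is at "Month 12 (±2 weeks) after Baseline". The extension entry visit may be held on the same day, in which case "assessments already outlined in Visit 8 study protocol 43USSA1812 only need to be performed once", or separately within the next 2 weeks. GAIS, satisfaction, FACE-Q and the Blinded Evaluator's rating are marked at both visits.

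**The concern.** Protocol section 2.3 gives the purpose of the extension as long-term data "beyond the Month 12 duration of the pivotal study 43USSA1812". For Group B, which gets no further treatment, that is a question about durability, and durability is read from Month 12 onward. A programmer who worked from SAP section 2.4.2 alone would produce rates at Months 19, 21 and 24 against Day 1 and might give no Month 12 column. A reader could then see that benefit is present at Month 24 but not whether it had faded.

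The pivotal report might not fill the gap. Its Month 12 rate covers everyone seen at that visit, whereas the extension population holds only those who went on to enrol.

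There is also a question of which record counts. A Group B subject can have one or two sets of assessments around Month 12, and the readable text does not say which one is the Month 12 value.

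Finally, at the same study month the two groups are about a year apart in time since first treatment, which a reader of side-by-side columns could miss.

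**Working it through.** There is no planned figure to reproduce: the extension has no sample size calculation and no test. The check compares the texts and then sizes what would be lost if Month 12 were left out.

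**Does the protocol rule survive?**
- Protocol section 10.4 contains both the list of GCWS months and the all-time-points rule. In the sponsor's own text, then, naming endpoint months does not limit what is presented.
- SAP section 2.4.2 repeats the list and is silent on the rule. It does not say that only those months are shown.
- SAP section 2.1 displaces the protocol where there are differences. An unrepeated sentence is not a difference, so the rule stands. For Group B, the span from Day 1 to Month 24 includes Month 12.
- The data exist. Completing Month 12 is an inclusion criterion (protocol section 5.2), and Group B's Day 1 values already have to come from the pivotal database.

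**What would be lost if Month 12 were dropped?** The rates here are assumptions, because the documents give none. Suppose 55 of 100 Group B subjects respond at Month 24. The Clopper-Pearson 95% interval is 44.7% to 65.0%. That summary is the same whether the Month 12 rate was 55% (no loss) or 75% (a loss of 20 points).

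**Could the pivotal rate stand in?** Suppose 70 of 100 Month 12 completers respond and *k* do not enter the extension. The entrants' Month 12 rate then lies between (70 − k)/(100 − k) and 70/(100 − k):

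| k | Lowest | Highest |
|---|---|---|
| 0 | 70/100 = 70.0% | 70/100 = 70.0% |
| 5 | 65/95 = 68.4% | 70/95 = 73.7% |
| 10 | 60/90 = 66.7% | 70/90 = 77.8% |
| 20 | 50/80 = 62.5% | 70/80 = 87.5% |

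These are extremes, with every non-entrant a responder or every one a non-responder. Both documents expect about 150 subjects in the extension, and the protocol synopsis gives about 150 for the pivotal study as well. That is the k = 0 row.

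**Weeks since first treatment** (1 month = 4 weeks; Day 1 taken as first treatment in Group B; entry visit 0 to 2 weeks after the pivotal Month 12 visit):
- Group A Month 24: 48 ± 2 = 46 to 50.
- Group B Month 12: 48 ± 2 = 46 to 50.
- Group B Month 24: (46 to 50) + (0 to 2) + (46 to 50) = 92 to 102.
- Group B Month 19, protocol Table 2 (+2 weeks): (46 to 50) + (0 to 2) + (28 to 30) = 74 to 82.
- Group B Month 19, SAP Table 2 (±2 weeks): (46 to 50) + (0 to 2) + (26 to 30) = 72 to 82.

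The gap between the groups at the same study month comes from the design. It follows from the group definitions and from the reference points given in SAP sections 1.3 and 2.4.2.

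**How much hangs on the Month 12 record?** With a same-day visit there is one record, and protocol section 4.7.1 lets the pivotal Month 12 visit serve as the entry visit. With separate visits there are two records at most 2 weeks apart, at 46 weeks or more after first treatment. Either is a fair Month 12 value.

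**The case for a change.** The strongest case for a change is that a SAP should be sufficient for the programmer. One who works from section 2.4.2 alone could omit Month 12, and the SAP does not say whether its silence counts as a difference from the protocol. Restoring the protocol sentence would still not settle which of two records is Month 12. Read strictly, visits after Month 12 would leave an entry-visit row holding only subjects with a separate entry visit. If that were 20 of 100, a 70% rate (14/20) would have an interval of 45.7% to 88.1%, against 60.0% to 78.8% for 70/100. The remedy would cost a few lines and no new data.

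Part of this stands. The SAP does not name the record, and one confirming sentence would be harmless. The rest is weaker. Omission requires setting aside a protocol rule that nothing contradicts. It also presumes that Month 12 is missing from the companion table formats (SAP section 2.1.2) and from the redacted exploratory text, neither of which can be read and neither of which may be counted as absent. The 20-subject row depends on one reading of the visit wording, against protocol section 4.7.1, and on an invented share of separate visits. The pivotal Month 12 rate may come from a different set of subjects, but nothing shows that it will.

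Time-since-treatment labels or a Month 12 by Month 24 cross-tabulation could help a reader. They are extra displays in a descriptive study, and SAP section 2.1.2 allows supportive analyses to be added without an amendment.

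**Conclusion.** No change to the plan is needed. Followed as written, the two documents together present Group B's Month 12 result in the extension population, alongside sound rates at Months 19, 21 and 24 against Day 1. The missing tie-break is a detail between records no more than 2 weeks apart. A programmer would reasonably take the pivotal Month 12 value and use the entry-visit value only if that is missing.

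No endpoint, stated figure or error rate depends on the point. The conclusion rests on reading the SAP's silence as leaving protocol section 10.4 in force, which is the natural reading because that section holds both statements without conflict. If the final tables did omit Month 12, the loss would be one descriptive column that can be rebuilt from pivotal data already needed for Day 1. The response and entry rates used above are assumptions for scale only.
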